The following adverse events (AEs) constitute absolute contraindications to further administration of R21/Matrix-M™. If any of these AEs occur during the study, the participant must not receive additional doses of R21/Matrix-M™ but may continue other study procedures at the discretion of the investigator. It is expected that the participant would continue full safety monitoring procedures, as per protocol.

- Acute allergic reaction or anaphylactic shock following the administration of vaccine investigational product.
- Pregnancy
- Any other findings that the investigator feels would increase the risk of having an adverse outcome from participation in the trial.

B5.8 Pregnancy

Participants are informed that the safety of the vaccine in pregnancy is unknown. Female study participants of childbearing potential are asked to use appropriate contraceptive methods to prevent pregnancy while they receive vaccinations. (Costs for contraceptives will be reimbursed by the study.) Appropriate contraceptive methods include:

- Established use of oral, injected or implanted hormonal contraceptives

**Research Proposal Submission Form
for a study involving human subject enrollment WITH
specimen collection**

Document No.: FTM ECF-033-01

Page 15 of 52

- Intrauterine Device or Intrauterine System
- Barrier methods (condoms or diaphragm with additional spermicide)
- Male sterilisation of an exclusive partner (with appropriate post-vasectomy documentation of absence of sperm in the ejaculate)
- True abstinence, when this is in line with the preferred and usual lifestyle of the subject. Periodic abstinence (e.g., calendar, ovulation, symptothermal, post-ovulation methods) and withdrawal are not acceptable methods of contraception.

Female participants will be tested for pregnancy immediately prior to each vaccination.

Should a participant become pregnant during the trial, she will be followed up as other volunteers and in addition will be followed until pregnancy outcome, with the participant's permission. We will not routinely perform venepuncture on such participants.

B5.9 Multi-site research - N/A

B6. RESEARCH METHODOLOGY

B6.1 Details of study design

Summary of Trial Design

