Vaccine and study medication accountability, storage, and handling will be in accordance with local SOPs. This study will not be blinded; i.e. it is an open-label study.

B6.2.2 Accountability of the study agents

The study site will maintain a record of the numbers of all vaccines and DHA/PIP + primaquine tablets obtained, used by the participants and returned to the pharmacy room in CTU. On study completion, a copy of the drug accountability record will be filed in the study folder.

B6.2.3 Concomitant medications

There will be no restrictions on concomitant medication beyond the exclusion criteria listed above.

B6.3 Study Endpoints

B6.3.1 Primary Endpoints

The safety of the investigational vaccine in each group:

- Occurrence of solicited from the date of each vaccination to 7 days of each vaccination.
- Occurrence of unsolicited adverse events (AEs) from the date of the first vaccination to 28 days after the last vaccination, according to the MedDRA classification.
- Occurrence of serious adverse events (SAEs) during the whole study period, i.e. during a 6-month follow up period from the receipt of first vaccination, according to the MedDRA classification.

B6.3.2 Secondary Endpoints

- For Arms 1 and 2, the concentration of antibodies against *Plasmodium falciparum* circumsporozoite (anti-NANP total IgG antibody), one month after the first dose (at Study month 1), one month after the second dose (at Study month 2), one month after the third dose (at Study Month 3) and six months after the first dose (at Study Month 6).
- Exploratory immunology endpoints including but not limited to cellular immunity.
- For Arms 1 and 3, piperaquine levels following the administration of the antimalarials with or without vaccine. (timepoints)

B6.4 Details of procedures for specimen/data collection

Procedures will be performed at the time points indicated in the schedule of procedures (Table 5). Additional procedures or laboratory tests may be performed, at the discretion of the investigators if clinically necessary (e.g. follow up repeat haematology or biochemistry laboratory tests in the event of clinically significant abnormal results).

Research Proposal Submission Form for a study involving human subject enrollment WITH specimen collection

Document No.: FTM ECF-033-01

Page 20 of 52

Table 5. Study Procedures

Timepoints	Month Day of month	Scr.	Study period																	
			M0				M1				M2				M3	M6 ^a				
			0 ^c	1	2	7	0	1	2	7	0	1	2	7	0	0				

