Informed Consent		x																		
Eligibility screen		x																		
Inclusion / Exclusion criteria		x	x				x				x									
Enrolment			x																	
Allocation			x																	
Interventions	Vaccination (Group 1 and Group 2)		x				x				x									
	DHA/piperazine (Group 1 and Group 3)		x	x	x		x	x	x		x	x	x							
	PQ (single low dose primaquine) (Group 1 and Group 3)		x				x				x									
Assessments	History of fever, current axillary temperature*	x	x	x	x	x	x	x	x	x	x	x	x	x	x	x				
	Full medical history, vital signs, physical examination	x	x				x				x									
	Ask about any concomitant medication	x	x	x	x	x	x	x	x	x	x	x	x	x	x	x				
	Assessment of any adverse event(s)		x	x	x	x	x	x	x	x	x	x	x	x	x	x				
	Assess for any withdrawal criteria		x	x	x	x	x	x	x	x	x	x	x	x	x	x				
	Blood tests						Unit (mL)													
	P. falciparum test**						0.5				0.5					0.5				
	CBC	2	2			2				2				2						
	Biochemistry ALT, AST, CREA, BUN, Bilirubin	3	3			3				3				3	3					
	HBsAg, HCV, HIV	1																		
	Immunology panel ^b		20				20				20				20	20				
	Piperazine levels***		1	1	1	1	1	1	1	1	1	1	1	1						
	Blood volume per visit (mL)	6	26	1	1	6	21.5	1	1	6	21.5	1	1	6	25	20.5				
	Maximum cumulative blood volume (mL)															144.5				
Electrocardiogram (ECG)		x																		

**Research Proposal Submission Form
for a study involving human subject enrollment WITH
specimen collection**

Document No.: FTM ECF-033-01

Page 21 of 52

Urine pregnancy test	x	x				x				x					
Diary card provided		x				x				x					
Diary card return						x				x					x

* Axillary temperature will be recorded from D0-D7 visits after each vaccination. If the symptoms are indicated to COVID-19, COVID-19 test will be done. If COVID-19 positive is indicated, then hospital guideline for COVID-19 case management will be followed. Study team will make decision whether or not to withdraw volunteer from the study case by case.

** *P. falciparum* test for purposes of indicating whether volunteer has been exposed, and not as an assessment of protection.

*** Piperaquine levels for group 1 and 3 only. Additional drug level assessment for Primaquine will be done, if additional data are required. Blood sample will be collected before each dose (at each visit) and then at day 7 for drug levels assessment.

- a. first day of M6
- b. the immunology panel consists of assays to be processed at UK laboratories and may include:

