 - Serology total IgG, IgG avidity, subclasses and isotypes against full length R21, CS C-term, NANP and HBsAb.
 - Functional assays to measure antibody function
 - Flow cytometry assays effector and memory T cells (e.g. CD4+ and CD8+), T follicular helper cells, regulatory T cells, B cells, plasma cells and dendritic cells
 - Enumeration of antibody-secreting cells (e.g. B and plasma cells)
 - Antibodies against viral pathogens including cytomegalovirus.
 - Other ELISA assays for immunity to malaria.
- c. If interval between screening and M0D0 is 7 days or less, screening lab results (haematology, biochemistry, *P. falciparum* test, and urine pregnancy test) can be used for enrolment (M0D0).

Table 6. Summary of participant visits

Group	Number of visit	Visit time points														
		Scr.	M0				M1				M2				M3	M6
			D0	D1	D2	D7	D0	D1	D2	D7	D0	D1	D2	D7	D0	D0
1	15	x	x	x	x	x	x	x	x	x	x	x	x	x	x	x
2	9	x	x			x	x			x	x			x	x	x
3	15	x	x	x	x	x	x	x	x	x	x	x	x	x	x	x

All the study procedures will be performed by the research team including research doctor, research nurse and research physician at the Clinical Therapeutics Unit at Faculty of Tropical Medicine, Mahidol University.

Table 7. Intervals between study visits

Interval	Optimal length of interval	Allowed interval
Screening to Month 0 / Day 0 (1 st vaccination)	0 to 7 days	-
Month 0 / Day 0 (1 st vaccination) to Month 1 / Day 0 (2 nd vaccination)	28 days	+/- 7 days
Month 1 / Day 0 (2 nd vaccination) to Month 2 / Day 0 (3 rd vaccination)	28 days	+/- 7 days
Month 2 / Day 0 (3 rd vaccination) to Month 3 / Day 0	28 days	+/- 7 days

**Research Proposal Submission Form
for a study involving human subject enrollment WITH
specimen collection**

Document No.: FTM ECF-033-01

Page 22 of 52

Day 7 after each vaccination	7 days	+/- 1 day
Month 3 / Day 0 to Month 6 / Day 0	84 days	+/- 14 days

B6.4.1 Recruitment

Volunteers will be recruited using methods previously successfully employed by the Clinical Therapeutics Unit (CTU) of the Mahidol-Oxford Tropical Medicine Research Unit. The volunteer unit maintains a register of candidates who expressed interest in the past to participate in clinical trials. In addition, volunteers will be recruited via flyers.

B6.4.2 Screening and Eligibility Assessment (Screening Visit)

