All potential volunteers will have a screening visit, which may take place up to 7 days prior to enrolment. Once informed consent is given, a screening number will be assigned in sequential order. Screening numbers will be issued consecutively (e.g. R21-001, R21-002, R21-003 etc.). This will be recorded in the Case Screening Form, together with the demographic information and procedures performed to determine eligibility. Screening procedures indicated in the schedule of procedures (Table 5) will be undertaken. If a screening haematology or biochemistry test result is out of the normal range, it may be repeated to ensure it is not a single occurrence. If an abnormal finding at screening is considered to be clinically significant, the volunteer will be informed, appropriate medical care arranged with the permission of the volunteer and the volunteer will be excluded from the study. In the unlikely event that a volunteer is found to have malaria or anaemia, the volunteer will be treated according to national guidelines and will be excluded from participating in the study.

B6.4.3 Enrolment and Baseline Assessment

All inclusion and exclusion criteria will be checked before enrolment in the study. Physical examination will be performed. Any new medical issues or symptoms that have arisen will be assessed. Blood will be collected for baseline *P. falciparum* test, clinical hematology and biochemistry. Blood will be collected and stored for measurement of antibodies against *P. falciparum* circumsporozoite (anti-CS antibody) until shipment to the reference laboratory. Urine will be collected from women of child-bearing potential for immediate pregnancy test.

If the interval between screening and enrolment is 7 days or less, the screening test results (*P. falciparum* test, haemoglobin, biochemistry, and urine pregnancy test) can be used for enrolment evaluation. In such cases, the tests (*P. falciparum* test, clinical hematology, biochemistry, and urine pregnancy test) will not be repeated at the baseline (Month 0 / Day 0) visit.

If all inclusion criteria are fulfilled and none of the exclusion criteria apply, the patient will be enrolled into the study and a case record form (CRF) specific to each participant completed. Regimen allocation and administration of the vaccine will be on Day 0 Month 0. The randomization lists will

**Research Proposal Submission Form
for a study involving human subject enrollment WITH
specimen collection**

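### Protocol B5.8 requires a pregnancy test immediately before every vaccination, but B6.4.3 and Table 5 footnote c let a screening test up to 7 days old replace it at dose 1

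*Protocol*

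**What the plan says.** Section B5.8 of the protocol sets the general rule: "Female participants will be tested for pregnancy immediately prior to each vaccination". It makes no exception for the first dose, and it tells participants that the vaccine's safety in pregnancy is not known.

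Section B6.4.3, which covers the enrolment visit, first calls for an immediate urine test in women of childbearing potential and then waives it. The waiver opens "If the interval between screening and enrolment is 7 days or less, the screening test results" and lists the urine pregnancy test among the results that may be reused. It adds that in such cases the listed tests "will not be repeated at the baseline (Month 0 / Day 0) visit". Footnote c to Table 5, attached to the Month 0 Day 0 column header, gives the same allowance: the screening haematology, biochemistry, *P. falciparum* test "and urine pregnancy test) can be used for enrolment (M0D0").

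Dosing is on that day: "Regimen allocation and administration of the vaccine will be on Day 0 Month 0". Screening is a visit "which may take place up to 7 days prior to enrolment" (B6.4.2), and Table 7 gives the same window with no further allowance.

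Two related provisions do not conflict. Inclusion criterion 4 (B5.2.1) asks for a negative test before each vaccination but sets no time limit. Section B6.4.6 requires an immediate urine test before dosing at Months 1 and 2, with no waiver.

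**The concern.** The two rules cannot both be met at dose 1 when a site relies on a screening test from an earlier day. A test several days old is not one done immediately before vaccination. A site that uses the waiver departs from B5.8, and a monitor checking against B5.8 could record a deviation at each such first dose. Nothing in the protocol says which section prevails.

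The looser check also falls at first exposure, while doses 2 and 3 keep the strict one. Pregnancy is an exclusion criterion and, under B5.7, an absolute contraindication to further vaccination. In arm 1, dihydroartemisinin-piperaquine and primaquine start on the same day as the vaccine.

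**Working it through.** The plan states no figure to reproduce. The check compares the provisions and then sizes the gap.

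**1. The rules at each dose**

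| Dose | B5.8 | Visit-level rule |
|---|---|---|
| 1 (Month 0 Day 0) | Test immediately before vaccination | Screening test may be reused if 7 days old or less (B6.4.3; Table 5 footnote c) |
| 2 (Month 1 Day 0) | Same | Immediate test before dosing, no waiver (B6.4.6) |
| 3 (Month 2 Day 0) | Same | Immediate test before dosing, no waiver (B6.4.6) |

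The rules differ at dose 1 only. The Table 5 mark for a urine test on Month 0 Day 0 does not settle the matter, because footnote c already qualifies that column.

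**2. Who qualifies for the waiver**

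- Waiver condition: screening to enrolment of 7 days or less (B6.4.3).
- Permitted screening window: 0 to 7 days (B6.4.2; Table 7).

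The waiver limit equals the whole window, so every participant enrolled on schedule qualifies. The test relied on at dose 1 can be 0 to 7 days old. A same-day screening test can meet B5.8; one aged 1 to 7 days does not.

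**3. First doses open to the conflict**

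Vaccine is given in arms 1 and 2, so there are 50 + 50 = 100 first doses. Let *p* be the share of participants who are women of childbearing potential and *q* the share of those screened 1 to 7 days before dosing. The documents give neither. I assume *p* = 0.40 to 0.60 and *q* = 0.50 to 1.00.

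- Number open to the conflict = 100 × *p* × *q*
- Low: 100 × 0.40 × 0.50 = 20
- High: 100 × 0.60 × 1.00 = 60

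**4. Time between scheduled pregnancy tests**

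Table 7 puts dose 2 at 28 ± 7 days after dose 1, that is 21 to 35 days.

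- With a Month 0 Day 0 test: 21 to 35 days to the next test.
- Under the waiver, with a screening test 1 to 7 days old: 1 + 21 = 22 days to 7 + 35 = 42 days.

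The waiver therefore lengthens the interval by 1 to 7 days.

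**5. Extra tests if the waiver is removed**

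Over all three arms, with the same *p*: 120 × 0.40 = 48 to 120 × 0.60 = 72 tests at most.

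**The case against.** The strongest reply is that the waiver is an option. Screening results may be reused, and the statement that tests are not repeated can be read as covering only cases where the site has chosen to reuse them. On that reading, a site that tests on Month 0 Day 0 satisfies every section. The allowance also appears in two places and is absent for doses 2 and 3, which suggests that the sponsor meant it. What is missing may then be only a cross-reference in B5.8. The risk is low as well: a negative test within 7 days is always needed, contraception is required, planned pregnancy is excluded, and Table 5 marks "Inclusion / Exclusion criteria" for checking again on Month 0 Day 0. Finally, the 20 to 60 range rests on assumed shares.

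Much of this stands. A site can choose to comply with both rules, the risk is small, criterion 4 is met, and the counts are only illustrative. The conflict remains, though. A site that uses the allowance with a test from an earlier day still breaches B5.8, and B5.8 is itself specific about timing and about covering every dose. No other text reconciles the two. An intended allowance would explain the waiver, but B5.8 would still promise something different.

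**Conclusion.** The concern holds. As written, the protocol promises a pregnancy test immediately before each vaccination and, at the first dose, permits a test up to 7 days old. The contradiction follows from the text alone and needs no assumption.

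Its reach is narrow: one dose of three, in the two vaccine arms. The estimate of 20 to 60 affected first doses depends on the assumed shares and counts doses given on a test that does not meet B5.8; it does not count pregnancies exposed. The practical effect is a test 1 to 7 days older than B5.8 intends. This is a correction to a safety procedure that should be made. It has no bearing on the endpoints, the power or the analysis.

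**What to change.** Delete the urine pregnancy test from both lists in the B6.4.3 waiver and from Table 5 footnote c. A urine test would then be done on Month 0 Day 0, before first dosing, in every woman of childbearing potential; a screening test done that same day would count. Because allocation is also on Month 0 Day 0, do the test before allocation and in all three arms. Keep the waiver for haematology, biochemistry and the *P. falciparum* test. Inclusion criterion 4 needs no change.

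The cost is three short deletions and at most one repeat urine test per woman, at a visit that already takes place: no more than 48 to 72 tests across the trial under the 40-60% assumption.

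If the sponsor prefers to keep the 7-day rule, the minimum is to write the dose 1 exception into B5.8. That removes the contradiction but leaves the older test in use at first exposure.

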This study is a randomized, open-label, single centre, Phase 2 trial of R21/Matrix-M™ in healthy Thai adults. A total of 120 participants will be enrolled and randomized into one of three study arms in a ratio of 5:5:2 as described in Section 6.4.4. Each arm will have 50 participants (for arm 1 and 2) and 20 participants (for arm 3).

- For arm 1 and 3, the eligible volunteers will be asked to come into the Hospital for Tropical Diseases to receive the study agents as out-patient on Day 0 (the day of vaccination), Day 1, Day 2, and Day 7 of Study Months 0, 1 and 2; and on Day 0 of Study Months 3 and 6. There are a total of 15 study visits.
- For arm 2, the eligible volunteers will be asked to come into the hospital to receive the study agent (vaccination only) as out-patient on the day of vaccination (Day 0) and Day 7 of Study Months 0, 1 and 2; and on Day 0 of Study Months 3 and 6. There are a total of 9 study visits.

**Research Proposal Submission Form
for a study involving human subject enrollment WITH
specimen collection**

Document No.: FTM ECF-033-01

Page 16 of 52

Table 2. Vaccine and drug administration

Timepoints	Month Day of month	Scr.	Study period														
			M0				M1				M2						
			0	1	2	7	0	1	2	7	0	1	2	7			
Interventions	Vaccination (Group 1 and Group 2)		x					x						x			
	DHA/piperaquine (Group 1 and Group 3)		x	x	x			x	x	x				x	x	x	
	PQ (single low dose primaquine) (Group 1 and Group 3)		x					x						x			

B6.2 Investigational Products:

1) R21/Matrix-M™

Description of Vaccine: The candidate R21 vaccine to be used has been developed by Jenner Institute and manufactured under cGMP conditions at Serum Institute India Private Limited (SIIPL). R21 is produced to high levels in *Hansenula polymorpha* yeast in fermenters. The purified R21 antigen (drug substance) is released after testing, by SIIPL QC Department using qualified and validated methods. The quality released drug substance is used, for manufacturing drug product after appropriately diluting to 20 µg/mL using formulation buffer. The formulated blend is fill finished in siliconized glass vials (4 mL capacity) at a targeted concentration of not less than 20 µg/mL. Each vial is filled with 0.65 mL of the drug product to enable withdrawal of 0.5 mL. The final formulation has 20 mM Tris, 15% sucrose, 30 mM magnesium chloride, pH 7.4.

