1.4.3 Active questioning to detect adverse events and serious adverse events

As a consistent method of collecting AEs, the subject should be asked a non-leading question such as: 'Have you felt different in any way since receiving the vaccines or since the previous visit?'

When an AE/SAE occurs, it is the responsibility of the investigator to review all documentation (e.g. hospital progress notes, laboratory and diagnostics reports) relative to the event. The investigator will attempt to establish a diagnosis pertaining to the event based on signs, symptoms, and/or other clinical information. In such cases, the diagnosis should be documented as the AE/SAE and not the individual signs/symptoms.

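### Unsolicited AEs are asked about at six more contacts in Arm 1 than in Arm 2, all on Days 1-2, which can inflate the Arm 1 percentages by an unknown amount

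*Protocol*

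**What the plan says.** Protocol B6.1 has Arms 1 and 3 attend on Day 0, "Day 1, Day 2, and Day 7 of Study Months 0, 1 and 2", plus Months 3 and 6: "There are a total of 15 study visits". Arm 2 attends "on the day of vaccination (Day 0) and Day 7 of Study Months 0, 1 and 2", plus Months 3 and 6: "There are a total of 9 study visits". Table 6 confirms the schedule by group.

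Table 5 marks AE assessment at every visit after screening, including each Day 1 and Day 2 visit. Its footnote adds "Axillary temperature will be recorded from D0-D7 visits after each vaccination". Appendix B 1.4.3 makes questioning at contacts the standard way of collecting AEs: "the subject should be asked a non-leading question such as" the one it then gives, "Have you felt different in any way since receiving the vaccines or since the previous visit".

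Every participant also gets a diary card for solicited AEs, with room to write down unsolicited ones (B6.4.5). Diaries are reviewed at follow-up visits for both kinds of event, and symptoms not yet documented are recorded too (B6.4.7). The trial is open-label (B6.4.4).

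Unsolicited AEs up to 28 days after the last vaccination are a primary endpoint in protocol B6.3.1. SAP section 5 tabulates them by group with exact 95% confidence intervals. Neither document mentions the unequal number of contacts.

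**The concern.** The primary objective is safety with and without concurrent antimalarials, so Arm 1 v Arm 2 is the contrast readers will look for, even though SAP 5 plans no formal test. The protocol's sample-size section expects to see safety signals between arms.

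The arms cover the same calendar period but are not questioned equally often within it. A brief, mild event on Day 1 or 2 is asked about on the spot in Arm 1. In Arm 2 it is recorded only if the participant writes it down unprompted or recalls it five to six days later. Extra questioning can therefore push up the Arm 1 percentage with identical true rates.

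The unsolicited table is also where some real drug effects would appear. Dizziness (about 12%) and disturbed sleep are listed effects of DHA-PIP (protocol C2.1) but are not among the solicited events in Table 8. A true effect and an ascertainment effect would point the same way, and the plan has no means of telling them apart. Exact confidence intervals reflect sampling error only.

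**Working it through.** **1. Visit counts (B6.1, Tables 5 and 6).** Total = 1 screening + 3 rounds x visit days per round + Month 3 + Month 6.

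- Arms 1 and 3: 1 + 3 x 4 + 2 = 15, as stated.
- Arm 2: 1 + 3 x 2 + 2 = 9, as stated.
- Difference: 15 - 9 = 6 = 2 days (Days 1 and 2) x 3 rounds.
- AE contacts after screening: 14 v 8, a ratio of 1.75.
- AE contacts in Months 0-2: 12 v 6, a ratio of 2.
- AE contacts on Days 1-2: 6 v 0.

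**2. Possible size.** SAP 5 reports the percentage of subjects with at least one event. Let p be the chance that one extra contact brings out an AE that would otherwise go unrecorded, and b the proportion who have a recorded AE anyway. Someone already counted adds nothing, so, treating contacts as independent of each other and of b,

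excess in Arm 1 = (1 - b) x [1 - (1 - p)^6].

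The documents give neither p nor b. All values below are assumptions. One participant in an arm of 50 is 2 points.

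| p | 1 - (1 - p)^6 | Excess at b = 0 | Excess at b = 40% (x 0.6) | Participants of 50, b = 0 / b = 40% |
|---|---|---|---|---|
| 0.5% | 0.0296 | 3 points | 1.8 points | 1.5 / 0.9 |
| 1% | 0.0585 | 6 points | 3.5 points | 2.9 / 1.8 |
| 2% | 0.1142 | 11 points | 6.8 points | 5.7 / 3.4 |
| 5% | 0.2649 | 26 points | 15.9 points | 13.2 / 7.9 |

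The b = 0 column is an upper value for the percentage with any unsolicited AE. For a single preferred term b is small, but p for that term would be much smaller than p for any AE.

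**3. Which outcomes are exposed.**

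- Solicited AEs: the same diary, thermometer and tape measure in every arm, so little affected. The exception is temperature taken in clinic on Days 1-2.
- SAEs: unlikely to depend on a Day 1 or Day 2 question.
- Laboratory values: Table 5 schedules no haematology or biochemistry on Days 1-2, so the occasions are equal.
- Arm 1 v Arm 3: 15 visits each, so contact-matched.
- Unsolicited AEs, Arm 1 v Arm 2: exposed, mainly for mild events of short duration.

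**The case against.** The best defence is that Arm 2 is not unobserved on Days 1-2. The Appendix B question looks back to vaccination or the previous visit, so at Arm 2's Day 7 visit it covers the whole interval. The diary, which takes unsolicited events too, runs in every arm. Most reactions expected in the first two days (fever, nausea, headache, myalgia, local reactions) are solicited and so come through the diary. This stands. What differs is prompt questioning against recall and optional self-report, so only part of the unsolicited events can be lost.

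A second defence is that the consequence is limited. SAP 5 is descriptive, and the safety outcomes listed in SAP 3.2 are SAEs. This stands in part: protocol B6.3.1 still names unsolicited AEs as a primary endpoint, and side-by-side percentages will be read as a comparison. Arm 3 offers a contact-matched comparator for Arm 1, but it has 20 participants and no vaccine, so it cannot separate extra questioning from a vaccine-drug effect.

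A reader might infer that the main comparison should move to events from the diary and the common contacts. That would introduce an opposite bias. An Arm 1 event mentioned on Day 1 or 2 would be dropped, while the identical Arm 2 event reported on Day 7 would be kept. The loss falls in Arm 1 only, on the days DHA-PIP is given, and could hide a real effect such as dizziness. Such a table is useful only as a sensitivity analysis.

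**Conclusion.** The contact schedule is unequal (12 v 6 AE contacts in Months 0-2, 14 v 8 after screening). It can inflate unsolicited-AE percentages in Arm 1 relative to Arm 2, and neither document allows for it. The direction follows from the design, but the size cannot be known from the documents. Under the assumed p of 0.5% to 5%, the excess is 3 to 26 points at b = 0 and about 1.8 to 15.9 points at b = 40%.

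Two stronger readings are not supported. One is that the whole Arm 1 v Arm 2 safety comparison is biased: diary-solicited AEs, SAEs and scheduled laboratory values are little affected. The other is that an excess of some stated number of points should be expected: every p and b here is assumed, and the largest figure needs 5% of participants to yield a new, otherwise lost AE at each of six visits, with nobody already counted.

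The change is worth making because unsolicited AEs are a primary endpoint and the remedy is cheap. No visit needs to change.

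**What to change.** - **AE CRF:** if not already captured (the CRF is a separate document that is not available here), record for each unsolicited AE the source (diary or visit) and the contact at which it was first reported. Collect this as events are entered, because it may not be recoverable later.
- **Day 7 visit:** ask every arm the same question about the whole period since vaccination, so that Arm 1 is not asked only about the time since Day 2.
- **SAP 5:** keep the all-contact table as the main table. Add a pre-specified Arm 1 v Arm 2 sensitivity table of unsolicited AEs recorded in the diary or reported at common contacts (Days 0 and 7, Months 3 and 6). Count an event also reported at Day 7 even if it was first mentioned on Day 1 or 2.
- **Interpretation:** state that the all-contact table may over-count Arm 1 and the sensitivity table may under-count it. A difference seen only in the all-contact table should not be attributed to co-administration without that caveat.

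The cost is one CRF field, one table and a fixed wording at Day 7. The drawback is that the sensitivity table may omit real Day 1-2 events in Arm 1 only, which is why it sits beside the main table and does not replace it.
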